9.2. Setting

Patients previously followed in KIMS[®], new patients fulfilling the inclusion criteria and transition patients with confirmed childhood onset GHD will be asked to participate. All patients should be diagnosed with GHD according to the current medical standards, and treated with Genotropin as prescribed in clinical practice^{4,5}.

After having given their informed consent, the patient is enrolled in the study. The patient is treated according to clinical practice. Normal clinical practice may include routine diagnostic procedures such as; blood samples, CTs, MRI and other tests. The decision of what measures to perform is not pre-specified in the protocol but is based on the clinical experience, standards and judgment of the investigator. Data from patient records, which align with the data to be collected in the database eCRF as specified in this protocol, will be collected and entered into the database. The data will be collected during the patients' routine visits to the clinic.

The interval between each the patient's visits, duration of treatment and participation in the study for each individual are at the discretion of the investigator and the patient.

After informed consent has been obtained from the patient, background data are collected and if available in KIMS[®], all the data will be transferred automatically into the database. This includes but is not limited to medical history, laboratory, imaging and background data such as Genotropin dosing. Background information, includes: history of birth, family and medical history, pituitary diagnosis, growth, puberty, GH treatment before start in the study (if applicable).

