9.10. Study size

This is a descriptive study without a pre-specified hypothesis and calculation of sample size is not applicable. Approximately 900 patients are expected to be included.

The study is planned to continue for 5 years and each patient entering the study will be included for the whole time period if not prematurely with-drawn. Hence the total number will be in the range of 900 patients (600 from KIMS® and 250 new adult patients and 50 from the confirmed childhood onset GHD population).

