### 3.3 SUBGROUPS

- Adult patient of 18 years of age and above and diagnosed with Childhood onset GHD, labeled Childhood onset GHD (CO-GHD)
- Adult patient of 18 years of age and above, not in the CO-GHD group above and diagnosed with GHD before 2013 and previously treated with Genotropin and followed in KIMS®, labeled KIMS GHD (*K-AO-GHD*)
- Adult patient of 18 years of age and above, not in the CO-GHD group above and newly diagnose with GHD, labeled *Naïve-AO-GHD* (N-AO-GHD)

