## 4.2 EFFICACY/EFFECTIVENESS ENDPOINT(S)

There is no pre-specified endpoint, but the study collects information from adult subjects prescribed Genotropin in clinical practice.

Each patient will be classified according to his/her IGF-I assessments as follows (in hierarchy);

1. If any of the assessments of IGF-I after Swegho baseline visit, are less than the lower limit of normal (LLN), the patient will be defined as “*IGF-I LLN*”.
2. Else if any of the assessments of IGF-I after Swegho baseline visit, are greater than the upper level of normal (ULN), the patient will be defined as “*IGF-I ULN*”.
3. Else if the patient has no IGF-I reported after Genotropin start, the patient will be defined as “*IGF-I unknown*”.
4. Else the patient will be defined as “*within ref range*”.

Where appropriate, the summaries will be presented by subgroups as defined above.

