## 4.3 SAFETY ENDPOINTS

For each patient, the safety event reporting period begins at the time of the patient’s first dose of Genotropin® or the time of the patient’s informed consent if s/he is already exposed to Genotropin®, and lasts through the end of the observation period of the study, which must include at least 28 calendar days following the last administration of a drug under study. Most often, the date of informed consent is the same as the date of enrollment. In some situations, there may be a lag between the dates of informed consent and enrollment. In these instances, if a patient provides informed consent but is never enrolled in the study (e.g., patient changes his/her mind about participation), the reporting period ends on the date of the decision to not enroll the patient.

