**4.4 OTHER ENDPOINTS/ASSESSMENTS**

Detailed operational definitions for some endpoints/assessments are give below.

Age is defined as age at baseline.

Duration of study will be summarized by subgroup. Duration of study is defined as time from baseline to exit date.

CCI [Redacted]

[Redacted]

[Redacted]

CCI [Redacted]

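### The IGF-I classification in SAP 4.2 uses two time origins, so an already-treated patient with no follow-up IGF-I can be counted as within the reference range

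*SAP*

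**What the plan says.** SAP 4.2 sets no formal endpoint but classifies every patient by IGF-I, applying four rules in order.

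- Rule 1 opens "If any of the assessments of IGF-I after Swegho baseline visit, are less than the lower limit of normal (LLN"), and labels the patient *IGF-I LLN*.
- Rule 2 does the same for values above the upper limit, also counted from the SWEGHO baseline visit, and gives *IGF-I ULN*.
- Rule 3 reads "Else if the patient has no IGF-I reported after Genotropin start, the patient will be defined as" *IGF-I unknown*.
- Rule 4 is an unconditional remainder and gives *within ref range*.

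SAP 4.1 defines baseline as the baseline visit in the eCRF. The visible text does not define Genotropin start. SAP 4.4 begins "Detailed operational definitions for some endpoints/assessments are give below", but part of that section is blacked out.

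**The concern.** Rules 1 and 2 look forward from study entry. Rule 3 looks forward from the start of treatment, which for many patients came earlier. An IGF-I value between those two dates is too early to count as low or high, yet it is enough to prevent the *unknown* label. If the patient has no later value, only rule 4 remains, and it does not ask for an in-range result.

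A missing follow-up measurement would then appear as the reassuring category in the only classification under the SAP's efficacy/effectiveness heading. The error runs in one direction only. It also falls unevenly across the subgroup columns, which the SAP presents side by side, because it needs treatment to have begun before the baseline visit.

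**Working it through.** **1. Can the situation arise?**

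- Already-treated patients are eligible. Protocol 9.3 admits former KIMS patients, and SAP 3.3 gives them a column: "not in the CO-GHD group above and diagnosed with GHD before 2013 and previously treated with Genotropin and followed in KIMS".
- On-treatment values at or before baseline can be in the database. SAP section 4 lists IGF-I as a baseline variable, which alone is enough. Protocol 9.2 also transfers available KIMS data: "This includes but is not limited to medical history, laboratory, imaging and background data such as Genotropin dosing".
- A later value is not guaranteed. Protocol 9.2 states: "The decision of what measures to perform is not pre-specified in the protocol". Protocol 10.2 allows withdrawal at any time, and the full analysis set in SAP 3.1 does not require a follow-up visit.

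**2. Applying the rules to an already-treated patient with no IGF-I after baseline**

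| On-treatment IGF-I at or before baseline | Class as written | Class if rule 3 also requires a post-baseline value |
|---|---|---|
| None | unknown | unknown |
| Normal | within ref range | unknown |
| Low | within ref range | unknown |
| High | within ref range | unknown |

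With four states before or at baseline (none, normal, low, high) and the same four afterwards, there are 16 combinations. Only the last three rows above change class; the other 13 do not.

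**3. A finer enumeration.** Take four time points (before baseline, baseline visit, soon after baseline, one year), each none, low, normal or high: 4⁴ = 256 patterns. These are logical patterns, not patient frequencies. Suppose Genotropin started before all four.

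- LLN: any low value at the two later points, (16 − 9) × 16 = 112.
- ULN: no low and at least one high there, (9 − 4) × 16 = 80.
- No value at either later point: 16 patterns. One has no IGF-I at all and is *unknown*. The other 15 are *within ref range* as written.
- Of those 15, the number with no in-range value anywhere is 3 × 3 − 1 = 8.

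Correcting rule 3 moves exactly those 15 to *unknown*. LLN stays at 112 and ULN at 80. If Genotropin starts at baseline, no pattern changes.

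**4. Size.** The plan gives no figure to reproduce. Let m be the share of a column with the pattern in step 2, and p the in-range share among the rest, all assumed to have a follow-up value.

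- Reported share: p(1−m) + m
- True share of all patients: p(1−m), so the excess is m
- True share of assessable patients: p, so the excess is m(1−p)

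Both inputs are assumptions.

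| m | p | Reported | Of all | Of assessable | Excess over all (points) | Excess over assessable (points) |
|---|---|---|---|---|---|---|
| 2% | 80% | 80.4% | 78.4% | 80% | 2.0 | 0.4 |
| 5% | 80% | 81.0% | 76.0% | 80% | 5.0 | 1.0 |
| 10% | 80% | 82.0% | 72.0% | 80% | 10.0 | 2.0 |
| 10% | 60% | 64.0% | 54.0% | 60% | 10.0 | 4.0 |
| 10% | 90% | 91.0% | 81.0% | 90% | 10.0 | 1.0 |

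Patient counts cannot be derived. Protocol 9.10 planned 600 KIMS patients out of about 900, but SAP 2.1 reports around 340 enrolled in total and gives no split by subgroup.

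**The case against.** **The key term may be defined out of sight.** Part of SAP 4.4 is blacked out, and the table shells are in a separate document. If Genotropin start were defined there as the SWEGHO baseline visit, the problem would disappear. This cannot be excluded. The visible wording points the other way. The same list names the SWEGHO baseline visit when it means that date. SAP 4.3 also separates first dose from entry, starting the reporting period at "informed consent if s/he is already exposed to Genotropin".

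**SAP 5 leaves missing values out.** One could argue that a patient without follow-up IGF-I drops out under that general rule. But SAP 4.2 classifies every patient and has its own *unknown* class, and rule 4 assigns these patients a class. SAP 5 does not clearly rescue the rule.

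**The group may be small or empty.** This stands. Protocol 9.10 says: "The study is planned to continue for 5 years and each patient entering the study will be included for the whole time period", and one IGF-I at any time in follow-up takes a patient out of the group. SAP 4.1 selects yearly visits by their IGF-I value, which suggests that follow-up testing was expected.

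**The size is mostly algebra.** This also stands. The excess over all patients is simply the assumed m, so the table shows direction and scale, not an estimate.

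**More columns could be affected.** The newly diagnosed subgroup is defined by diagnosis, not by being untreated at baseline, and Protocol 9.3 requires Genotropin to be prescribed at inclusion. A newly diagnosed patient who started before the baseline visit could meet the same pattern. This widens the scope of the point.

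**Conclusion.** The concern holds on the plain wording, as a minor point. Followed literally, SAP 4.2 puts already-treated patients with no follow-up IGF-I in *within ref range* whenever an on-treatment value exists at or before the baseline visit, whatever that value was. Confidence in the mismatch is high; how many patients it affects is unknown and may be none.

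The effect is confined to descriptive percentages. It can arise in the KIMS adult-onset column, among previously treated patients in the childhood-onset column (which is assigned first), and among newly diagnosed patients who started before the baseline visit. Under the assumed ranges, m of 0–10% and p of 60–90%, the in-range share is overstated by 0–10 points of all patients or 0–4.0 points of assessable patients. LLN and ULN counts are correct as planned, SAP 6.1 rules out hypothesis tests, and SAP 4.1 lists every visit. The conclusion assumes that no unseen text equates Genotropin start with the baseline visit.

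**What to change.** Leave rules 1 and 2 unchanged. Reword rule 3 to assign *IGF-I unknown* when the patient has no IGF-I assessment dated later than both the SWEGHO baseline visit and Genotropin start. Rule 4 then covers only patients with at least one such assessment and no out-of-range value after the baseline visit. Define Genotropin start in SAP 4.2 if the blacked-out text does not already do so. Showing the number of assessable patients per column is optional.

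Rules 1 and 2 should not be moved to the later of the two dates. For a patient starting Genotropin between the soon-after-baseline and one-year points, that would reclassify 80 of the 256 patterns (48 LLN, 32 ULN), whereas the rule 3 edit changes none.

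The cost is one phrase in the SAP and a small programming change, with no new data. The *within ref range* share may fall slightly and *unknown* rise to match. If the sponsor already meant the baseline visit, no patient changes class and the ambiguity is removed.

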#### 4 ENDPOINTS AND COVARIATES

The patient is treated according to clinical practice. Normal clinical practice may include routine diagnostic procedures such as; blood samples, CTs, MRI and other tests. The decision of what measures to perform is not pre-specified in the protocol but is based on the clinical experience, standards and judgment of the investigator. Data from patient records, which align with the data to be collected in the database eCRF as specified in the study protocol, is collected and entered into the database. The data is collected during the patients' routine visits to the clinic.

Endpoints will be summarized at baseline and at follow up and change from baseline will be derived if appropriate.

Continuous data will be summarized using descriptive statistics where the following parameters will be reported:

- Number of observations (n),
- Mean,
- Quartile 1 (Q1),
- Median,
- Quartile 3 (Q3),
- Standard deviation (SD),
- Range (Min,Max)

Categorical data will be presented as the number and percentage of patients.

In general, all data will be listed. Summary tables will be structured with a column for each of the three subgroups defined in Section 3.3 and a column for the total if other not stated.

The following variables should be captured according to the Study Protocol (if available):

Variable	Role	Data source(s)	
Informed Consent (mandatory)	Before Baseline	Personally signed and dated Informed Consent Document	
BACKGROUND INFORMATION -Age -Gender - Ethnic origin (only CRF) -Age at menarche	Baseline		

-Menopause/Amenorre -Age at Menopause/Amenorrea -Puberty (Induced, Spontaneous) -Age at end of growth			
MEDICAL HISTORY -Hypertension -Claudication -Coronary Heart Disease -Stroke -Arthrosis -Diabetes -Type I -Type II -Epilepsy -Neoplasm -Other Significant disease -Fractures	Baseline	Patient record and or CRF	
FAMILY HISTORY -Diabetes -Cardiovascular Disease -Hip Fracture -Colon Polyps -Colon Cancer -Neoplasm (other)	Baseline	Patient record and or CRF	
PITUITARY DISEASE -Date of Diagnose -Childhood onset -Brain Tumor -Visual Field deficit -Ophthalmoplegia -Tumor treatment -Tumor Size -Tumor type	Baseline	Patient record and or CRF	
DIAGNOSE OF GHD -Date of Diagnose of GHD -Test method -Date of test	Baseline	Patient record and or CRF	
BASELINE PREVIOUS GH TREATMENT -Treatment start date -Treatment stop date	Baseline	Patient record and or CRF	

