EXAMINATION -Weight -Height -BMI -Blood pressure -Heart rate (Supine) -CT/MRI -Waiste, Hip -Body Composition -Additional Hormone Abnormalities	Baseline, Follow up visit	Patient record	
TREATMENT -GH treatment -Concomitant Medication of special interest	Baseline, Follow up visit	Patient record	
LABORATORY -Glucose -HbA1c -IGF-I	Baseline, Follow up visit	Patient record	
ADVERSE EVENT	Follow up visit	Patient record and information obtained from the patient	

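### SAP 4.2 starts the IGF-I *unknown* category from a different time point than the low and high categories, so a previously treated patient with no IGF-I value after baseline can be labelled *within ref range*

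*SAP*

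**What the plan says.** SAP 4.2 names no pre-specified endpoint but classifies every patient by IGF-I, in hierarchical order:

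- Item 1 begins "If any of the assessments of IGF-I after Swegho baseline visit, are less than the lower limit of normal (LLN" and gives the label *IGF-I LLN*.
- Item 2 begins "Else if any of the assessments of IGF-I after Swegho baseline visit, are greater than the upper level of normal (ULN" and gives *IGF-I ULN*.
- Item 3 begins "Else if the patient has no IGF-I reported after Genotropin start" and gives *IGF-I unknown*.
- Item 4 labels everyone left as *within ref range*.

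The summaries are shown by subgroup where appropriate.

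Four other places bear on who reaches item 4:

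- Protocol 9.3 admits patients already treated with Genotropin and followed in KIMS. Protocol 9.10 expects 600 of them among about 900.
- Protocol 9.2 says available KIMS data are transferred into the study database after consent: "This includes but is not limited to medical history, laboratory, imaging and background data such as Genotropin dosing".
- The variable table in SAP 4 lists "Glucose -HbA1c -IGF-I" for both baseline and follow-up visits, if available.
- No test is mandated. SAP 4 states "The decision of what measures to perform is not pre-specified in the protocol". Protocol 9.2 leaves visit intervals to the investigator and patient, and likewise "duration of treatment and participation in the study for each individual are at the discretion of the investigator and the patient".

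**The concern.** Items 1 and 2 use one time origin and item 3 uses another. The two coincide for a patient who starts Genotropin at the SWEGHO baseline. For a patient who was on Genotropin earlier, there is a gap between them. A value in that gap is enough to escape *unknown*, but it is never compared with the reference limits. Item 4 then asserts that the patient is in range without any value from the follow-up period behind it.

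This is the only classification spelled out under the SAP's effectiveness heading, and it is meant to be read across subgroups. Absence of follow-up data would be labelled *within ref range* in patients with an earlier on-treatment value and *unknown* in patients without one. Treatment history largely separates the subgroups in SAP 3.3, so two columns could differ in the in-range share with the same IGF-I control and the same amount of missing data.

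A lesser matter concerns how the label is read. One out-of-range value removes *within ref range* for good, so the label can only be lost as values accumulate, and the number of values is not fixed.

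**Working it through.** **Step 1. The rule applied literally.** The SAP states no figure for this classification, so there is none to reproduce. The related enrolment figure adds up: 600 + 250 + 50 = 900.

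| On-treatment value before or at baseline | Values after baseline | Item 1 | Item 2 | Item 3 | Label |
|---|---|---|---|---|---|
| in range | none | no | no | no | *within ref range* |
| below LLN | none | no | no | no | *within ref range* |
| above ULN | none | no | no | no | *within ref range* |
| none | none | no | no | yes | *unknown* |
| any or none | one, in range | no | no | no | *within ref range* |

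The first three rows have no value in the period that items 1 and 2 assess. Only the fourth is called unknown.

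**Step 2. How many patients.** Let *u* be the fraction of previously treated patients with an earlier on-treatment value and none after baseline. The documents do not give *u*; 5, 10 and 20% are assumptions. Mislabelled patients = *u* × group size.

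| *u* | 600 planned KIMS patients (Protocol 9.10) | two-thirds of 340, about 227 (SAP 2.1; share assumed from 600/900) |
|---|---|---|
| 5% | 30 | 11 |
| 10% | 60 | 23 |
| 20% | 120 | 45 |

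**Step 3. Effect on the reported share within the previously treated group.** Let *W* be the in-range share among patients with at least one post-baseline value. As written, the reported share is *u* + (1 − *u*)*W*. With item 3 aligned it is (1 − *u*)*W*, with *u* shown as unknown. The difference is *u*, whatever *W* is. For illustration, assume five values per patient, 2.5% per tail per value and within-patient correlation 0.6, which gives *W* = 0.833:

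| *u* | in range, as written | in range, aligned | unknown, aligned |
|---|---|---|---|
| 5% | 84.2% | 79.2% | 5% |
| 10% | 85.0% | 75.0% | 10% |
| 20% | 86.7% | 66.7% | 20% |

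**Step 4. Dependence on the number of values.** Assume probability *p* = 2.5% per tail per value and a stable patient mean. With *k* independent values, P(in range) = (1 − 2*p*)^*k*. With correlation, use a normal random intercept and integrate the *k*-th power of the conditional in-range probability over it.

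| Within-patient correlation | *k* = 1 | *k* = 2 | *k* = 5 |
|---|---|---|---|
| 0 | 95% | 90% | 77% |
| 0.6 | 95% | 91% | 83% |
| 0.9 | 95% | 93% | 90% |

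Five values is about what one selected visit per year would give over the planned October 2013 to October 2018 collection period. Independence is the extreme row, since repeated IGF-I values in one patient are likely to be correlated. The direction is the same in each row; the size shrinks as correlation rises.

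**The case against.** **SAP 5 excludes patients with missing values of an endpoint.** That could be read as removing patients with no post-baseline IGF-I. It does not clearly do so, because 4.2 has its own category for missing data and item 4 gives these patients a non-missing label.

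**The visit windows in SAP 4.1 apply to summary tables.** If they govern this table they limit the number of values per patient, but they do not change item 3. Section 4.2 speaks of any assessment and does not refer to the windows.

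***Genotropin start* may have been meant as start in the study.** This is possible, but the SAP does not say so, and the neighbouring items use a different term. If that was the intent, the wording still needs correcting.

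**An any-value label is a legitimate descriptive summary.** This stands. A reader might infer from Step 4 that the label is invalid and should be replaced. The documents do not support that. Its dependence on follow-up is visible from its definition, Protocol 9.10 plans that "each patient entering the study will be included for the whole time period if not prematurely with-drawn", SAP 4.1 already provides for yearly summaries with visit selection built around IGF-I, and SAP 4.4 shows study duration by subgroup. Nothing shows that testing frequency actually differs between subgroups.

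**Testing low before high hides some high patients.** A reader might infer that *IGF-I ULN* is materially understated. With five values and correlation 0.6 or more, the shortfall is at most 1.6% of ever-high patients for assumed tails of 2.5 to 10%, so it does not merit a change.

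**Conclusion.** The mismatch in item 3 is a definite error on the plain text of SAP 4.2. It needs only an on-treatment IGF-I value before or at baseline and none after it, which the protocol's data transfer and discretionary testing make possible. It is not confined to KIMS patients: anyone already on Genotropin with an on-treatment baseline value can be affected.

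Its size is unknown. The mislabelled share equals the share of previously treated patients in that position. The counts of 30 / 60 / 120 or about 11 / 23 / 45 rest on the assumed 5 / 10 / 20%, and the second set also on the assumed two-thirds KIMS share. Enrolment may have continued after the SAP was finalised.

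A reader might take the 600 as the size of a subgroup column, or the percentages in Step 3 as shares of all patients. Neither follows. SAP 3.3 moves childhood-onset patients, including any from KIMS, into their own group, and Step 3 describes previously treated patients only.

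The dependence on the number of values is real but secondary, and calls for extra display only. The study is descriptive, the SAP itself asks for cautious interpretation, every value is listed, and no hypothesis test or error rate is affected.

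**What to change.** 1. Reword item 3 of SAP 4.2 so that *IGF-I unknown* means no IGF-I value reported after the SWEGHO baseline visit. *Within ref range* then requires at least one post-baseline value and none out of range. Cost: one line of SAP text and the matching line of programming; no new data.
2. As a minor addition, show beside the label the number of post-baseline IGF-I assessments per patient, by subgroup. Also give a count of low, in range, high and no value for each yearly window, using the SAP 4.1 visit selection. Cost: a few table rows. The yearly count leaves out values from the first six months and from visits not selected; the existing label and the listings still cover these.

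The label itself and the order of items 1 and 2 can stay.

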9.8. Variables

The variables to be captured are listed in **Table 1**.

Table 1. Variables to be captured (if available).

Variable	Role*	Data source(s)
Informed Consent (mandatory)	Before Baseline	Personally signed and dated Informed Consent Document
BACKGROUND INFORMATION -Age -Gender - Ethnic origin -Age at menarche -Menopause/Amenorrea -Age at Menopause/Amenorrea -Puberty (Induced, Spontaneous) -Age at end of growth	Baseline	Patient record and or CRF
MEDICAL HISTORY -Hypertension -Claudication -Coronary Heart Disease -Stroke -Arthrosis -Diabetes -Type I -Type II -Epilepsy -Neoplasm -Other Significant disease -Fractures	Baseline	Patient record and or CRF
FAMILY HISTORY -Diabetes -Cardiovascular Disease	Baseline	Patient record and or CRF

-Hip Fracture -Colon Polyps -Colon Cancer -Neoplasm (other)		
PITUITARY DISEASE -Date of Diagnose -Childhood onset -Brain Tumor -Visual Field deficit -Ophthalmoplegia -Tumor treatment -Tumor Size -Tumor type	Baseline	Patient record and or CRF
DIAGNOSE OF GHD -Date of Diagnose of GHD -Test method -Date of test	Baseline	Patient record and or CRF
BASELINE PREVIOUS GH TREATMENT -Treatment start date -Treatment stop date	Baseline	Patient record and or CRF
EXAMINATION -Age -Weight -Height -Blood pressure -CT/MRI -Body Composition -Additional Hormone Abnormalities	Baseline, Follow up visit	Patient record
TREATMENT -GH treatment -Concomitant Medication of special interest	Baseline, Follow up visit	Patient record
LABORATORY -Glucose -HbA1c -IGF-I	Baseline, Follow up visit	Patient record
ADVERSE EVENT	Follow up visit	Patient record and information obtained from the patient

Detailed operational definitions will be included in the Statistical Analysis Plan.

*For patients previously treated in KIMS[®] historical data will automatically inserted into the Database.

Concomitant Medication of Special Interest:

It is recommended to collect all concomitant medication. The particular attention should be given to the following concomitant medication of special interest:

1. Replacement of other pituitary hormone deficits: sex steroids, glucocorticoids, thyroxine and vasopressin
2. Treatment of prolactin abnormalities
3. Antihypertensive drugs
4. Lipid lowering drugs
5. Anti-diabetic drugs
6. Antidepressant drugs
7. Anti-epileptic drugs

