9.9. Data sources

Data collected during the normal clinical practice is to be entered into the study database. Data from local labs and CT/MRI will be collected as available. Data will be manually entered or imported from archived patients records into the study database.

Information collected during the treatment and follow up of study patients is entered into eCRFs contained within Viedoc®, a password protected data entry and data management tool. Viedoc® will be made available to investigators through the Internet.

Data previously entered for a subject in KIMS® may be made available in the study provided that a new Informed consent, including permission to use KIMS® data, is signed by the subject.

A study patient code is generated by Viedoc® for each study patient at the time of their enrollment into the study. Only the treating investigator or an authorized staff member has access to patient identifiable information using the study patient code.

Each study investigator has ultimate responsibility for the collection and reporting of all clinical, safety and laboratory data entered on the eCRFs and any other data collection forms (source documents) and ensuring that they are accurate, authentic / original, attributable, complete, consistent, legible, timely (contemporaneous), enduring and available when required. The eCRFs must be signed by the study investigator or by an authorized staff member to attest that the data contained on the eCRFs are correctly recorded.

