## **5 HANDLING OF MISSING VALUES**

Patients with missing values of a particular endpoint will not contribute to the analysis.

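### SAP 4.2 makes 'within ref range' the leftover IGF-I class, so a patient with no scorable value after the Swegho baseline can be counted as in range

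*SAP*

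**What the plan says.** SAP 4.2 sets up a hierarchy that covers everyone: "Each patient will be classified according to his/her IGF-I assessments as follows (in hierarchy").

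- Rule 1 gives the low class: "If any of the assessments of IGF-I after Swegho baseline visit, are less than the lower limit of normal (LLN").
- Rule 2 gives the high class, where any assessments after the Swegho baseline "are greater than the upper level of normal (ULN), the patient will be defined as" 'IGF-I ULN'.
- Rule 3 is the only route to 'IGF-I unknown': "Else if the patient has no IGF-I reported after Genotropin start, the patient will be defined as" unknown.
- Rule 4 has no condition: "Else the patient will be defined as" 'within ref range'.

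The laboratory rows of Protocol Table 1 (9.8) and of the SAP section 4 table name only "Glucose -HbA1c -IGF-I". Protocol 9.9 adds: "Data from local labs and CT/MRI will be collected as available". The only missing-data rule is SAP 5: "Patients with missing values of a particular endpoint will not contribute to the analysis". No readable section says where the limits come from or what happens when one is absent.

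**The concern.** 'Within ref range' is the favourable class, yet no patient has to show anything to enter it. It takes whoever rules 1 to 3 do not catch. Two kinds of patient can arrive there without a single value shown to lie within limits.

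- **Values without usable limits.** Rules 1 and 2 cannot be met without a limit. Rule 3 does not apply, because an IGF-I value was reported.
- **Values only before or at the Swegho baseline.** Rules 1 and 2 look after the Swegho baseline, but rule 3 looks after Genotropin start. A patient already on treatment, with earlier IGF-I results and none since the baseline visit, has nothing for rules 1 and 2 to examine and is not 'unknown' under rule 3.

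This is the only outcome classification that the readable SAP defines, and it sits under the effectiveness heading. SAP 6.1 rules out hypothesis tests and SAP 4.5 has no covariates, so the reported percentage is itself the result.

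**Working it through.** The documents give no figure for this classification, so there is nothing to reproduce. The check has two parts.

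**1. Applying the rules literally.** The test patients use made-up limits of 100 and 300. The last column requires at least one value after the Swegho baseline with both limits before a patient is called within range.

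| IGF-I data | SAP 4.2 as written | Positive definition |
|---|---|---|
| 50, both limits | LLN | LLN |
| 400, both limits | ULN | ULN |
| 200, both limits | within | within |
| 50, no limits | within | unknown |
| 400, no limits | within | unknown |
| 400, LLN only | within | unknown |
| 400 with limits, before Swegho baseline only | within | unknown |
| 200 with limits, plus 400 without | within | within |
| no IGF-I at all | unknown | unknown |

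Four rows change, all from 'within' to 'unknown'. Patients whose post-baseline values all carry limits keep their class. The row with one scorable and one unscorable value does not change, so a fix must also say how partly missing limits are handled.

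**2. Size of the effect of missing limits.** Take patients with IGF-I values after the Swegho baseline. Let m be the share whose values have no usable limits, and q the share within range among the rest. Then:

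- reported within-range share = q(1 − m) + m
- excess over the scorable share = q(1 − m) + m − q = m(1 − q)

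Neither m nor q is in the documents. Over an assumed range, the excess in percentage points is:

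| q | m = 0 | m = 5% | m = 10% | m = 20% | m = 30% |
|---|---|---|---|---|---|
| 50% | 0 | 2.5 | 5 | 10 | 15 |
| 60% | 0 | 2 | 4 | 8 | 12 |
| 70% | 0 | 1.5 | 3 | 6 | 9 |
| 90% | 0 | 0.5 | 1 | 2 | 3 |

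For example, with q = 60% and m = 10%, 0.6 × 0.9 + 0.1 = 64% is reported against 60% among scorable patients. For scale only, 10% is 34 of the roughly 340 patients included when the SAP was finalised (SAP 2.1), or 90 of the 900 expected (Protocol 9.10).

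As an error against the truth, m(1 − q) also assumes that unscorable patients are in range as often as the others. The direction does not need that assumption: a missing limit can never remove a patient from 'within ref range'.

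**The time-anchor route** is additional and does not vanish when limits are complete. Protocol 9.10 expects 600 of the 900 patients from KIMS, and Protocol 9.2 and 9.7 transfer their KIMS data into the study database. Earlier IGF-I values can therefore be present. How many such patients have none after the Swegho baseline is not stated.

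**The case against.** The strongest reply is that the unscorable patient may not exist. The variable tables are not field lists. Blood pressure is one entry, yet SAP 4.3.2 splits it into systolic and diastolic. Adverse event is one entry, yet SAP 4.3.1 lists dates, seriousness, causality, action and outcome. Limits may therefore be held in the eCRF, and the redacted part of SAP 4.4 or the separate TLF plan may define them. This stands. A reader might infer from the tables that LLN and ULN are not collected, and the documents do not support that.

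A second reply is that SAP 5 already drops such patients, if the endpoint is taken to be the classification. That reading is possible but does not clearly close the gap. The IGF-I value is present, and SAP 4.2 classifies each patient. It also keeps an 'unknown' class, which would have little purpose if patients without a usable result were dropped.

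A third reply is that the stakes are modest: SAP 4.2 says there is no pre-specified endpoint, and SAP 4.1 puts all visits in listings. This is true and limits the harm, but the summary table would still carry the label.

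None of these replies touches the wording itself. Rule 4 is unconditional and the two time anchors differ, and both are fully readable.

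**Conclusion.** The point holds as a defect in the stated rule. SAP 4.2 assigns 'within ref range' by default, and so labels as in range any patient whose post-baseline values lack usable limits or whose only IGF-I values precede the Swegho baseline visit or were taken at it.

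Missing limits can only raise the within-range count. The excess is m(1 − q), which is zero if every value has its limits. Its actual size is unknown, and the tabulated figures illustrate assumed values of m and q.

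Three stronger readings are tempting and should not be drawn:

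- That IGF-I control is in fact overstated. No document shows that any limit is missing.
- That the excess can be judged in standard errors at n = 340. That number is enrolment when the SAP was finalised, not the number with IGF-I after baseline, and the study is descriptive.
- That the subgroup columns are distorted. This would need recording of limits to differ between sites or subgroups, on which the documents are silent.

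**What to change.** Amend SAP 4.2 as follows.

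- Use the Swegho baseline visit as the time anchor in every rule.
- Keep rules 1 and 2. Then define 'within ref range' positively: at least one IGF-I value after the Swegho baseline with both LLN and ULN, and all such values between them.
- Send every patient not classed as LLN, ULN or within range to 'IGF-I unknown'.
- State that a value with one limit or none is not scored against the missing limit, and report how many such values there are. This makes visible the patient who is called within range on only some of the values.
- State whether percentages include the unknown class. With q = 60% and m = 10%, the within-range share would be 0.6 × 0.9 = 54% of all these patients, or 60% of the scorable ones.

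Confirm that LLN and ULN are captured with each IGF-I value, and query missing limits before the database lock that SAP 6.1 places ahead of any presentation.

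The cost is a few lines of SAP text and one data query. The 'unknown' count may rise and the within-range share may fall. Patients whose post-baseline values all have limits keep their class.
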